6.11.3 Exploratory Efficacy Analyses

6.11.3.1 Change from Baseline in physical function status (PROMIS)

All PROMIS records will be listed by participant, visit, and questionnaire type (self-report/parent proxy).

Actual values and change from baseline will be summarized by visit and confirmed objective response status for each PROMIS Scale, with self-report and parent proxy records summarized separately. The summaries presented will be the mean, SD, median, minimum, and maximum values.

Box and whiskers plots of change from baseline will be presented by visit for each scale separately.

6.11.3.2 Change in Functional Impairments

Change from baseline in functional impairments, measured according to Section 4.1.3.2, will be summarized by visit and age cohort.

In participants who have tumors that affect functional status at baseline, the change from baseline in muscle strength and range of motion in the PN affected areas, as described in Section 4.1.3.2, will be presented by visit.

In addition, for all physical functioning assessments, plots will be created for scores at each visit. This will be presented individually for each participant, as well as all being included in a whole population plot.

All recorded functional impairment data of any form will be listed.

6.11.3.2.1 Strength

For each of the individual strength assessments, to assess the change from baseline at a visit, a participant will need assessments in which all the following categories, as assessed at baseline, match at that visit:

- Side affected
- Position during assessment (sitting/supine/lateral decubitus)
- Muscle group assessed

Assessment of strength will be conducted only in the area affected by the target tumor. Measurements will be obtained using Medical Research Council (MRC) grading followed by quantitative assessments using the sponsor provided MicroFET2 dynamometer.

The MRC grading will be presented by each affected area summarizing the number and percent of participants in each category below:

Document: S:\Q_146\Q_03974\MEK-NF-201\Prog_Stat\Documentation\SAP\MEK-NF-201 SAP v1.0.0.docx
Author:

0 – No movement is observed.

- 1 Only a trace or flicker of movement is seen or felt in the muscle or fasciculations are observed in the muscle.
- 2 Muscle can move only if the resistance of gravity is removed. As an example, the elbow can be fully flexed only if the arm is maintained in a horizontal plane.
- 3 Muscle strength is further reduced such that the joint can be moved only against gravity with the examiner's resistance completely removed. As an example, the elbow can be moved from full extension to full flexion starting with the arm hanging down at the side.
- 4 Muscle strength is reduced but muscle contraction can still move joint against resistance.
- 5 Muscle contracts normally against full resistance.

The strength measured by the dynamometer by each area location will be summarized and the percent change from baseline using standard summary statistics will be summarized by age cohort and by visit.

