8.1.3. Strength Assessment

All participants with a target PN that causes motor dysfunction or weakness will undergo a focused evaluation of strength of the affected muscle groups in accordance with the SoA (Section 1.3) during the Treatment Phase. The contralateral side will be tested for comparison. This evaluation should be performed by Rehabilitation Medicine, Physiatry, or Physical Therapy, if possible, and should ideally be completed by the same examiner at each visit, if feasible.

Strength should be assessed utilizing a Sponsor provided dynamometer and Medical Research Council (MRC) Muscle Scale. The MRC grading assessment should be conducted prior to the dynamometer assessment. Dynamometer assessment and MRC grading (0-5/5) must be conducted in accordance with the study reference manual.

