4.1.3.2.2 Strength Assessments

All participants with a target PN that causes motor dysfunction or weakness at baseline will undergo a focused evaluation of strength of the affected muscle groups in accordance with the SoA (Sections 1.3-1.4 of the protocol) and will be included for this analysis. Strength will be assessed utilizing a Sponsor provided dynamometer and Medical Research Council (MRC) Muscle Scale. The MRC grading assessment should be conducted prior to the dynamometer assessment. Dynamometer assessment and MRC grading (0-5/5) must be conducted in accordance with the study reference manual. For each participant, the sum of the scores for the muscle groups tested will be taken as an overall score for each visit.

Document: S:\Q_146\Q_03974\MEK-NF-201\Prog_Stat\Documentation\SAP\MEK-NF-201 SAP v1.0.0.docx
Author:

4.1.3.2.3 6-Minute Walk Test

Participants with a target PN that causes airway or lower extremity motor dysfunction at baseline will undergo a 6-minute walk test in accordance with the SoA (Sections 1.3-1.4 of the protocol) that will be included for this analysis. Additionally, pulse rate, systolic blood pressure and diastolic blood pressure will be collected following a 5-minute rest after the 6-minute walk test is completed.

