5.3 Covariates

No covariates will be considered for the primary efficacy analysis. For all mixed models for repeated measures (MMRM) used in secondary and exploratory analyses, the only covariate included will be the respective baseline score.

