6.11.3.2.2 Range of Motion

For the range of motion assessments, to assess the change from baseline at a visit, a participant will need assessments in which all three categories, as assessed at baseline, match at that visit:

- Joint assessed
- Motion tested
- Type (passive/active)

The range of motion for that location will be summarized and the percent change using standard summary statistics will be summarized by age cohort and by visit.

6.11.3.2.3 6-Minute Walk Test

Participants with a target PN causing airway or lower extremity motor dysfunction at baseline will be assessed for change in 6-minute walk test distance. Vital signs are performed prior to the start of the walk test. The object of this test is to walk as far as possible over 6 minutes. After completing the test, participant will be instructed to rest for 5 minutes, after which time vital signs are repeated. The total meters walked will be captured. Standard summary statistics of length walked and the pre-/post vitals will be summarized by each visit.

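### The SAP drops the contralateral strength comparison the protocol requires, so exploratory strength and walk-distance change in children cannot be separated from normal growth

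*SAP*

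**What the plan says.** Protocol 8.1.3 covers participants whose target tumor causes motor dysfunction or weakness. Of the strength test it says "The contralateral side will be tested for comparison". Section 8.1.5 has the same instruction for range of motion.

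SAP 6.11.3.2.1 says "Assessment of strength will be conducted only in the area affected by the target tumor". The affected side appears there only as a key for matching a visit to its baseline, together with position and muscle group. The planned dynamometer output is: "The strength measured by the dynamometer by each area location will be summarized and the percent change from baseline using standard summary statistics", by age cohort and visit. The parent section, 6.11.3.2, adds: "Change from baseline in functional impairments, measured according to Section 4.1.3.2, will be summarized by visit and age cohort". SAP 4.1.3.2.2 defines a total in which "the sum of the scores for the muscle groups tested will be taken as an overall score for each visit", without saying which side counts.

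For the walk test, SAP 6.11.3.2.3 plans an assessment of change in distance and states: "Standard summary statistics of length walked and the pre-/post vitals will be summarized by each visit". No percent change is planned for it.

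No functional analysis uses height, age or reference values. SAP 5.3 says of the repeated-measures models that "the only covariate included will be the respective baseline score", and no such model is planned for strength or walking. The historical-control comparison covers time to progression and progression-free survival only.

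**The concern.** The exploratory objective is worded as the effect of the drug on function. In a single-arm study, a change from baseline can speak to that objective only if little else would have moved the measurement. In growing children something else does: force and walking distance rise with body size. Splitting results at age 18 leaves growth inside the pediatric cohort untouched. Percent change does not remove it either, because growth acts on the numerator and not on the baseline value.

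The protocol had already provided a partial internal comparator for strength, the other limb of the same child. Under the SAP those measurements would appear, at most, in listings. The wording also leaves two practical questions open: whether sites or programmers should treat contralateral values as part of the strength data at all, and whether they enter the summed score.

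**Working it through.** **1. Length of follow-up.** Cycle 24 Day 21 is study day (24 − 1) × 28 + 21 = 665, which matches the tumor and PRO visit-window tables in SAP 5.6. With the SAP's own conversion, 665 / 365.25 × 12 = 21.8 months.

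**2. Height gain.** Inputs are the middle height columns of protocol Tables 12 and 13 (the blood-pressure charts in Section 10.11). Elapsed time from Day 1 is 664 days, or 664 / 365.25 = 1.818 years. Height at the end is interpolated linearly between yearly entries.

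Example, a girl aged 6: the chart gives 118.4 cm at 6, 124.9 at 7 and 130.6 at 8. Height at 7.818 years = 124.9 + 0.818 × (130.6 − 124.9) = 129.6 cm. The ratio r = 129.6 / 118.4 = 1.094.

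| Start age | Girls, cm | Gain | Boys, cm | Gain |
|---|---|---|---|---|
| 6 | 118.4 to 129.6 | 9.4% | 118.9 to 129.9 | 9.3% |
| 7 | 124.9 to 134.7 | 7.8% | 125.1 to 135.3 | 8.2% |
| 8 | 130.6 to 140.0 | 7.2% | 131.0 to 140.4 | 7.2% |
| 9 | 135.6 to 146.6 | 8.1% | 136.3 to 145.5 | 6.7% |
| 10 | 141.0 to 153.5 | 8.9% | 141.3 to 151.6 | 7.3% |

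The same method gives up to 13.6% from age 2. The charts end at age 12, so they say nothing about participants who start at 11 to 17.

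**3. From height to strength and distance, with no drug effect.** The documents give no scaling. Assume strength goes with height to the power k; the gain is then r^k − 1.

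- k = 2: from 1.067² − 1 = 14% (boys aged 9) to 1.094² − 1 = 20% (girls aged 6). At ages 6, 8 and 10 alone the range is 15% to 20%.
- k = 3: about 22% to 31%.
- Walk distance with k between 0.5 and 1: about 3% to 9%.

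**4. Earlier visits, k = 2, ages 6 to 10.** At Cycle 5 (day 127) the gain is about 2.5% to 4%. At Cycle 13 (day 351) it is about 7% to 11%.

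**5. What the ratio does.** Let A be affected-side force and C contralateral force for the same muscle group and position. If both limbs grow in proportion, follow-up gives (A × r^k) / (C × r^k) = A / C. Growth then contributes 0% whatever k is. The ratio cannot help the walk test, which has no second side.

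**The case against.** A reader might infer that the plan credits growth to the drug as benefit. The documents do not support that. These endpoints are exploratory, the summaries are descriptive, and there is no test, threshold or success rule. What the documents do support is weaker: the planned summaries cannot tell the two apart.

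The size is also open to challenge, fairly. The scaling exponents are assumed, the heights come from general charts and not from children with NF1, and the largest figures belong to the last visit. Adolescents near final height would show less, and the number of children with motor or airway dysfunction is not stated.

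Other planned outputs are less exposed. MRC grade is capped at 5 and judged against gravity and examiner resistance, and range of motion is a joint measure. Individual plots and listings of all functional data are planned too. This narrows the point to dynamometer force and walk distance.

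The most serious objection is to making the ratio the outcome in place of affected-side change. It stands, for three reasons:

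- Inclusion criterion 3 admits extremity lesions with limb hypertrophy, so the two limbs need not grow alike.
- The contralateral limb receives the same systemic drug. Protocol 2.3 reports muscle weakness (in events seen mainly at higher doses), and Table 4 has an entry for it. If C falls while A is unchanged, A / C rises and looks like improvement.
- Protocol 4.2 describes faster tumor growth in younger children, so a weak limb that merely keeps pace with growth might itself reflect benefit.

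The ratio is therefore a supportive view, to be read beside both of its components.

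Finally, the word for area in the SAP sentence could mean muscle group and not side. That softens the conflict with protocol 8.1.3, but the comparison is still absent from the SAP.

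**Conclusion.** The point holds in a limited form. The SAP sentence does not sit with protocol 8.1.3, and the SAP plans no use of the contralateral measurements that the protocol requires. In the pediatric cohort, unadjusted change in dynamometer strength and walk distance is confounded with growth over 21.8 months.

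The height gain of about 7% to 9% for starting ages 6 to 10 rests on the protocol's charts and linear interpolation. The strength figure of about 14% to 20% at the last visit rests in addition on the height-squared assumption and should be read as an illustration. The walk-distance figure rests on an assumed exponent as well.

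The consequence is confined to how exploratory functional results in children can be interpreted. The primary endpoint is not touched, and nor are the adult results. The change is worth making because it uses data already required and lets the strength summary answer its stated objective better.

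**What to change.** 1. Reword the sentence in SAP 6.11.3.2.1 to agree with protocol 8.1.3: the affected muscle groups are assessed, and the contralateral side is tested for comparison.
2. State in SAP 4.1.3.2.2 that the summed score uses affected-side muscle groups only.
3. For participants aged 2 to 17 with a one-sided deficit, add a supportive summary of change from baseline in the affected-to-contralateral dynamometer ratio, matched on muscle group, position and visit.
4. Keep the planned affected-side change. Summarise the contralateral values next to it, so that a fall in the contralateral limb, or an effect of limb hypertrophy, can be seen.
5. Label pediatric strength and 6-minute-walk changes as not growth-adjusted. Distance divided by height at the visit may be shown as an added descriptive view only: it assumes linear scaling and would over-correct if the true exponent is below 1. Protocol 1.3 schedules height at the same visits as the walk test.

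The cost is SAP wording and one extra table, with no new data collection. Participants with bilateral deficits cannot contribute to the ratio and stay in the planned summaries only.

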6.11.3.2.2 Range of Motion

For the range of motion assessments, to assess the change from baseline at a visit, a participant will need assessments in which all three categories, as assessed at baseline, match at that visit:

- Joint assessed
- Motion tested
- Type (passive/active)

The range of motion for that location will be summarized and the percent change using standard summary statistics will be summarized by age cohort and by visit.

6.11.3.2.3 6-Minute Walk Test

Participants with a target PN causing airway or lower extremity motor dysfunction at baseline will be assessed for change in 6-minute walk test distance. Vital signs are performed prior to the start of the walk test. The object of this test is to walk as far as possible over 6 minutes. After completing the test, participant will be instructed to rest for 5 minutes, after which time vital signs are repeated. The total meters walked will be captured. Standard summary statistics of length walked and the pre-/post vitals will be summarized by each visit.

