	Tolerability will be assessed according to toxicities graded by National Cancer Institute (NCI) Common Terminology Criteria for Adverse Events (CTCAE) Version (v) 5.0;
To determine the duration of response;	Duration of response for participants whose best response is complete response (CR) or PR using centrally read MRI volumetric analysis;
To evaluate the effect of mirdametinib (PD-0325901) on quality of life as measured by patient-reported outcomes (PROs); and	Change from Baseline in quality of life (QoL) assessed by the age specific Pediatric Quality of Life Inventory (PedsQL); and
To evaluate the effect of mirdametinib (PD-0325901) on pain as measured by patient-reported outcomes.	Change from Baseline in pain (assessed using the Numeric Rating Scale-11 [NRS-11] and Pain Interference Index [PII]) in the Treatment Phase.

Tertiary/Exploratory				
To evaluate the effect of mirdametinib (PD-0325901) on physical functioning as measured by PROs;	Change from Baseline in physical function status (Patient-Reported Outcomes Measurement Information System [PROMIS] – Physical Function/Mobility/Upper Extremity Scale) in the Treatment Phase;			
To determine Baseline functional impairments secondary to PN, and the effect of mirdametinib (PD-0325901) on functional outcomes depending on PN location;	Change in localized strength (dynamometer and Medical Research Council Muscle Scale), range of motion, and endurance (6-minute walk test) of PN associated functional impairment in the Treatment Phase;			
To determine time to progression (TTP) and progression free survival (PFS) in progressive PN;	TTP and PFS in progressive PN (≥ 20% increase in PN volume within 12 months prior to first dose of study treatment) using centrally read MRI volumetric analysis;			
To assess TTP of mirdametinib (PD-0325901) versus historical controls;	Time until Progressive Disease (defined as PN increase ≥ 20% compared to Baseline) using centrally read MRI volumetric analysis;			
To evaluate the effect of mirdametinib (PD-0325901) on PN associated disfigurement;	Change from Baseline in PN-associated disfigurement using standardized photography;			
To correlate MRI responses with Pharmacodynamic (PD) biomarkers in PN biopsies obtained pre- and post-treatment with mirdametinib (PD-0325901);	Change in levels of pERK and other applicable biomarkers in tumor biopsies at Baseline and Cycle 24 / Early Termination (ET) visit; and			

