- 4. Participant has a target PN that is deemed inoperable, defined as a PN that cannot be completely surgically removed without risk for substantial morbidity due to: encasement of or close proximity to vital structures, invasiveness, or high vascularity of the PN, or the participant refuses surgery. Participants who previously underwent surgery for a PN will be eligible to enter the study after the surgery, provided the PN was incompletely resected and is evaluable by volumetric analysis;
- 5. Participants must have a target PN, defined as the clinically most relevant PN, amenable to volumetric MRI analysis. For the purpose of this study, the target PN must be seen on at least 3 consecutive MRI slices and the field of view must contain the entire tumor of interest. As determined by central radiologic review, a target PN must be analyzable by volumetrics using the REiNS criteria, at least 5 mL in volume, and will be classified as "typical PN", "nodular PN", or "solitary nodular PN" prior to first dose of study treatment;
- 6. Participants ≥ 18 years of age must have a PN amenable to a percutaneous biopsy and must be willing to undergo pre-, and end of treatment tumor biopsies providing fresh tumor tissue; there should be no contraindication for serial biopsy; Participants 2 to 17 years of age should not undergo biopsy unless there is a clinical indication to obtain fresh tumor tissue;
- 7. Participants ≥ 16 years of age must have a Karnofsky performance level of $\geq 50\%$, and participants < 16 years must have a Lansky performance of $\geq 50\%$. Note: Participants who are unable to walk because of paralysis, but who are upright in a wheelchair, will be considered ambulatory for the purpose of assessing the performance score;
- 8. Participant has adequate organ and bone marrow function as defined by the following Screening laboratory values:
 - 8.1. Absolute neutrophil count $\geq 1500 \text{ cells/}\mu\text{L}$;
 - 8.2. Platelets $\geq 100 \text{ x } 10^3/\mu\text{L}$;
 - 8.3. Hemoglobin \geq 9.5 g/dL;
 - 8.4. Serum albumin $\geq 2.8 \text{ g/dL}$;

8.5. Calculated creatinine clearance at Screening ≥ 60 mL/min (by Cockcroft-Gault formula) OR a normal serum creatinine based on age described in the table below;

Age (years)	Maximum Serum Creatinine (mg/dL)
≤5	0.8
$>$ 5 and \leq 10	1.0
> 10 and ≤ 15	1.2
> 15	1.5

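### By location, the only change summary the SAP names for range of motion and dynamometer strength is percent change, which has no value at a zero baseline and an unstable mean at low ones

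*SAP*

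**What the plan says.** Protocol Section 3, Table 1 lists the exploratory endpoint as "Change in localized strength (dynamometer and Medical Research Council Muscle Scale), range of motion" and 6-minute walk endurance. It is stated as change, not percent change.

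The SAP handles this at two levels.

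- **Overall.** Section 6.11.3.2 says "Change from baseline in functional impairments, measured according to Section 4.1.3.2, will be summarized by visit and age cohort". For participants with tumors affecting function it adds: "the change from baseline in muscle strength and range of motion in the PN affected areas, as described in Section 4.1.3.2, will be presented by" (the unit here is the visit). Both sentences refer to Section 4.1.3.2, where each participant's range-of-motion results, and the scores of the muscle groups tested, are summed into one score per visit.
- **By location.** For strength, Section 6.11.3.2.1 says: "The strength measured by the dynamometer by each area location will be summarized and the percent change from baseline using standard summary statistics". The breakdown is per age cohort and visit. For motion, Section 6.11.3.2.2 says: "The range of motion for that location will be summarized and the percent change using standard summary statistics will be summarized by age cohort". The same visit breakdown applies. Both sections first require that a follow-up assessment match baseline (side, position and muscle group; or joint, motion and passive/active type) before change can be assessed.

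Section 5.1.2 defines the default statistics as n, mean, SD, median, minimum and maximum. I found no rule for a zero or near-zero baseline in 4.1.3.2, 5.5 or 6.11.3.2. Section 5.5 limits imputation to the cases it lists, and functional assessments are not among them.

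**The concern.** Only participants whose target tumor causes motor dysfunction or weakness have these assessments, so low baselines are plausible. The MRC scale in Section 6.11.3.2.1 has a grade 0, defined as "No movement is observed". A muscle at that grade would give no active motion and no dynamometer force.

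Percent change copes badly with such baselines in three ways:

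1. At a zero baseline it has no value, so a participant who regains movement contributes nothing to that row.
2. At a small baseline a modest gain becomes a very large percentage, and a few participants can set the mean.
3. Random error in the baseline sits in the denominator and pushes the mean upward when nothing has changed. In a single-arm study there is no control group to subtract this.

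What is at stake is how the functional tables are read. No test or decision rests on these summaries.

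**Working it through.** The documents give no measurement error, baseline distribution or expected change for either measure, so there is no plan figure to reproduce. All error sizes and baseline values below are assumptions.

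**Step 1. Which change is planned at which level.** Section 6.11.3.2 plans change from baseline and points to 4.1.3.2, which defines only a summed score. Sections 6.11.3.2.1 and 6.11.3.2.2 work by location, and the only change statistic they name is percent change. Absolute change by joint or muscle group may be implied by the matching rules, but it is not stated.

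**Step 2. Zero baseline.** Percent change = 100 × (Y − X)/X, with X the baseline and Y the follow-up. At X = 0 it is undefined. Absolute change, Y − X, is defined.

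**Step 3. Influence of small baselines.**

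- Nine participants unchanged at 90 degrees and one going from 2 to 12 degrees: mean percent change = (9 × 0 + 500)/10 = +50%; median 0%; mean absolute change = 10/10 = +1 degree.
- Eighteen participants at 90 degrees and two at 5 degrees, all gaining 10 degrees: mean percent change = (18 × 11.1 + 2 × 200)/20 = 600/20 = +30%. The two low-baseline participants supply 400/600, or two thirds. Median +11.1%; mean absolute change +10 degrees.

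**Step 4. Mean percent change with no true change.** With independent errors in X and Y, E[100(Y/X − 1)] = 100(E[Y]·E[1/X] − 1). For X > 0 this is above zero by Jensen's inequality. With lognormal error it equals 100 × CV².

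- Force: CV 10% gives 100 × 0.10² = +1.0%; CV 20% gives 100 × 0.20² = +4.0%. The simulated median is about 0 in both cases.
- Motion: 2,000,000 simulated pairs per case, additive error, values rounded to whole degrees and floored at 0:

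| True range (degrees) | Mean % change, SD 3 | Mean % change, SD 5 | Baseline recorded as 0, SD 3 / SD 5 |
|---|---|---|---|
| 90 | +0.1 | +0.3 | 0% / 0% |
| 40 | +0.6 | +1.6 | 0% / 0% |
| 20 | +2.5 | +8.2 | 0% / 0% |
| 10 | +13.4 | +39.4 | 0.1% / 2.9% |
| 5 | +33.8 | +36.0 | 6.7% / 18.4% |
| 0 | −36.6 | −22.4 | 56.6% / 54.0% |

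The approximation 100 × (SD/true range)² agrees where error is small relative to range: (3/90)² gives 0.11% and (5/90)² gives 0.31%. The median was 0 in every row except 5 degrees with SD 5 (−25%) and 0 degrees (−100%). Mean absolute change stayed within 0.01 degree of zero throughout.

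**Step 5. Mixed cohort and summed score.** Eighteen participants at 90 degrees and two at 5 degrees, no true change, SD 3: mean percent change +3.3%, with median and absolute change about 0. If percent change were taken instead on a sum of three motions, the bias would be only +0.07% (true sum 190 degrees) to +0.25% (105 degrees).

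**The case against.** The strongest reply is that absolute change is already planned and percent change is one display among several. Section 6.11.3.2 commits to change from baseline in strength and motion. The matching rules in the two subsections suggest that change is derived location by location. A reader might therefore say that the remedy restates the plan. This stands in part, since absolute change is not absent. But the pointer to 4.1.3.2 leads to the summed score, and the subsections name only percent change, so the by-location absolute summary remains unstated.

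Two stronger readings are tempting, and the documents do not support them.

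- **That the most impaired participants are left out of the analysis.** They would be missing only from the percent-change rows. They remain in the location value summaries, the MRC counts, the plots and the listings. MRC grade 0 need not mean zero passive motion. The protocol's wording "Participants who are unable to walk because of paralysis" comes from a note on performance scoring and does not show that an assessed joint starts at zero.
- **That the functional result is biased toward improvement.** The upward drift concerns the mean of one display, is negligible at mid-to-large baselines, and reverses among defined values at a true zero. The planned median is largely protected, and the planned maximum would expose an extreme value.

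Percent change also has a real use in a study running from age 2 to adulthood, because raw force changes are hard to compare across body sizes. That supports keeping it as a supplement. It does not support making it the only change summary named by location.

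**Conclusion.** The point holds as an inexpensive improvement to an exploratory, descriptive analysis. By location, percent change is the only change summary named. It has no value at a zero baseline and no rule for that case, and its mean is unreliable when baselines are low. The drift in the mean with no true change is trivial at 90 degrees and noticeable at 20 degrees and below. These sizes rest on the assumed errors (SD 3 to 5 degrees; CV 10% to 20% for force). Whether the tables would be materially affected depends on how many baselines are low, which cannot be found from the documents. The primary endpoint is not affected.

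**What to change.** In SAP 6.11.3.2.1 and 6.11.3.2.2, state absolute change from baseline as the lead summary for each muscle group (dynamometer units) and each joint-motion (degrees), by age cohort and visit, including participants with a zero baseline. Keep percent change as a supplement, reported as median and quartiles, with the number excluded for a zero baseline. In 6.11.3.2, say whether change from baseline refers to the summed score, the location-level results or both.

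The cost is SAP wording and one more set of table rows, with no new data. Raw force changes compare less well across body sizes, and the retained percent change covers that.
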